1.0 Study Summary

Study Title	Non-invasive Vagal Nerve Stimulation in Opioid Use Disorders
Study Design	Sham controlled, two groups
Primary Objective	Map physiology of vagal nerve stimulation in patients with OUDs
Secondary Objective(s)	Study #1 maps effect of varying durations of vagal nerve stimulation (nVNS) on craving and sympathetic function; Study #2 explores neurophysiology of nVNS or sham stimulation paired with drug cues.
Research Intervention(s)/ Investigational Agent(s)	Study #1 involves open label dose finding (varying durations of nVNS). Study #2 involves randomization to non-invasive vagal nerve stimulation (nVNS) or sham control stimulation with assessment of brain, behavioral, physiological, and biomarker responses to drug cues and/or craving.
IND/IDE #	IND 52220
Study Population	Men and women with a history of Opioid Use Disorders (OUDs)
Sample Size	N=20 for study 1 and n=20 for study 2
Study Duration for individual participants	2-3 study visits, 6 week follow up call
Study Specific Abbreviations/ Definitions	Non-invasive Vagal nerve stimulation (nVNS or VNS), Opioid Use Disorders (OUDs)

2.0 Objectives*

- 2.1 The purpose of this study is to measure neural and biomarker correlates of vagal nerve stimulation (VNS) in men and women with a history of Opioid Use Disorders (OUDs). In the UG3 phase we will have two studies, Study #1 will be to optimize dosing (N=20) and Study #2 to measure brain and biological correlates of nVNS versus sham in conjunction with exposure to drug use cues (N=20). We will proceed to the UH3 phase which is a larger study in OUD patients if the goals of the UG3 phase are met per NIDA. Only the UG3 phase is covered here.
- 2.2 Brain function will be measured with positron emission tomography (PET) and biomarkers will be measured in blood, with an assessment of a broad range of stress responsive sympathetic, hormonal and immune markers
- 2.3 We hypothesize a decrease in sympathetic function and enhanced anterior cingulate function with VNS.

3.0 Background*

- 3.1 Opioid Use Disorders (OUDs) are highly prevalent and potentially lethal conditions (21). OUDs are often linked to trauma and posttraumatic stress disorder (PTSD) (2-20) and limited treatment options exist (21-25) the use of nVNS in this project during the opioid withdrawal period represents a new innovation from the current treatments using medication and counseling, widely acknowledged to have limitations for this critical period (26-31). Treatments are needed that address the underlying neurobiology of OUDs involving the sympathetic nervous system, inflammation, and brain areas and systems mediating craving and addiction like dopamine and the anterior cingulate, all potential targets of VNS (32-68, 73-94). VNS is effective for a number of conditions, including depression and epilepsy (69-72) and is effective for the underlying neurobiology of OUDs (96-244). Earlier generations of VNS devices had limited implementation due to the requirement for surgical implantation, cost, inconvenience, and the inability to do placebo comparisons related to ethical considerations (95). The failure of Medicare and therefore other insurance agencies to reimburse for VNS implantation has been a major limitation to date (95). Further innovation lies in the use of HR-PET imaging of the brain with equivalent resolution but lacking technical challenges related to interference of VNS electrical signal with scan acquisition using magnetic pulses seen with fMRI. Use of wearable sensing devices for measurement of sympathetic and parasympathetic function and modelling approaches for verification and

PROTOCOL TITLE: Non-invasive Vagal Nerve Stimulation in Opioid Use Disorders

exploration of stimulation parameters represent additional innovations made possible by our collaborations with the Georgia Institute of Technology and the City University of New York. We have a multi-disciplinary and diverse research team of investigators with expertise in engineering, computer sciences, behavior, radiology, modelling, nuclear physics, neuroimmunology, psychiatry, epidemiology, cardiology and biostatistics.

- 3.2 Our preliminary data on the effects of non-invasive Vagal Nerve Stimulation (nVNS) on stress response in traumatized human subjects and patients with posttraumatic stress disorder (PTSD) show that nVNS reliably blocks peripheral sympathetic and enhances parasympathetic function, reduces inflammatory responses (interleukin-6, or IL-6), and enhances central brain responses (anterior cingulate) to stress (72). We now propose to apply this technology to the treatment of patients with OUDs. Following verification using modelling and determination of optimal dosing parameters, we will use these parameters to assess effects of nVNS versus sham stimulation on opioid craving, peripheral autonomic, cardiovascular, inflammatory, and brain functional responses measured with High-Resolution Positron Emission Tomography (HR-PET) and radiolabeled water to videos of drug cues in recently treated patients with OUDs.
- 3.3 This project will assess a new device, non-invasive Vagal Nerve Stimulation (nVNS), that does not require surgery or implantation, and that electrically stimulates the vagus nerve as it passes through the neck, dampening the sympathetic nervous system and modulating brain regions in a way that may help patients during the opioid withdrawal period and reduce relapse. Studying the effects of nVNS on opioid craving and brain and physiological responses in patients with OUDs has the potential to reduce relapse and save lives, as well as increase our knowledge of changes to the brain and physiology that underlie OUDs and successful response to treatment.

4.0 Study Endpoints*

- 4.1 The primary study endpoint is subjective drug craving and change in neurophysiological variables (enhanced anterior cingulate function, increased pre-ejection period (PEP) and photoplethysmogram (PPG) amplitude, both indicating decreased sympathetic function).

5.0 Study Intervention/Investigational Agent

- 5.1 Description: This study assesses nVNS versus a sham stimulation effects on behaviors of drug craving with and without exposure to

PROTOCOL TITLE: Non-invasive Vagal Nerve Stimulation in Opioid Use Disorders

drug cues as well as brain response, neurophysiology and biomarkers. NVNS is applied to the neck and electrically stimulates one of the cranial nerves (the vagus) as it passes through the carotid sheath, exerting effects centrally in the brain and peripherally on autonomic and inflammatory function

- 5.2 Drug/Device Handling: Active nVNS and sham control are kept by research staff under lock and key and only used for the purposes of the study under supervision of the research coordinator.
- 5.3 The nVNS device has been approved by the Emory IRB for use in a current study in patients with PTSD. It is non-invasive with minimum side effects and has been shown to be well tolerated and there have been no adverse events or untoward effects in 56 subjects to date.

6.0 Procedures Involved*

- 6.1 Study Design: Study #1: This is a randomized dose finding study of nVNS versus sham stimulation in patients with a history of Opioid Use Disorders (OUDs). This study will optimize dosing (N=20) by testing different stimulation duration parameters. We will measure how these different parameters affect drug craving using analogue scales (248) as well as physiological signals with wearable sensing devices.

6.2

Study #2 is also in patients with OUDs whose aim is to measure brain and biological correlates of nVNS versus sham in conjunction with exposure to drug use cues (N=20). Active and sham devices are assigned serial numbers by ElectroCore Inc. and delivered to the Data Manager who keeps the blind and assigns to subjects as they are recruited using a random number generator. Subjects then undergo nVNS or sham over one day in conjunction with control neutral versus drug use videos to stimulate craving in conjunction with nVNS or sham with brain imaging, measurement of biomarkers and collection of wearable sensing device data. We proceed to the UH3 phase which is a larger study in OUD patients if the goals of the UG3 phase are met per NIDA. Only the UG3 phase is covered here. We hypothesize a decrease in sympathetic function and interleukin 6 (IL-6, an inflammatory marker) enhanced anterior cingulate function with VNS.

- 6.3 All subjects undergo assessment with behavioral measures, including the SCID (245, 246), a craving measure called the Clinical Opiate Withdrawal Scale (COWS) (248), the SHAPS-C, NRS pain scale, Addiction Severity Index, The Snaith Hamilton Pleasure Scale-Clinician (251), the Subjective Units of Distress Scale (263) The Visual Analogue Scale (VAS) consists of 10-point lines anchored with "not at all" on one end and

PROTOCOL TITLE: Non-invasive Vagal Nerve Stimulation in Opioid Use Disorders

"extremely" on the other where participants report the extent to which they felt any craving for opiates, severity of withdrawal symptoms, and the extent to which the study intervention has helped to ease the cravings.

Medical History, is taken with a structured questionnaire which assess socio-demographic factors, medical history, handedness, history of substance use, medications including antidepressants, mood stabilizer and antipsychotics, usage will be quantitated for number of years of usage for utilization in additional analyses. Urine drug testing may be done at study visits. The Early Trauma Inventory (ETI) is 56-item instrument for measurement of childhood traumatic experiences which has been shown to be reliable and valid. All subjects will be assessed with both the ETI-SF-SR for events before the age of 18 and the Adult Trauma Inventory (ATI) for after age of 18. Reinforcement Learning Task (Positive and Negative Valence Domain): Measures reward attainment using an instrumental conditioning task (90 trials). Trials for this task involve a 3s cue presentation during which subjects choose between two abstract stimuli, followed by an exponentially jittered delay, and then a 3s feedback presentation with positive (monetary win), negative (monetary loss) or neutral outcomes. Reward Motivation Task (Positive Valence Domain): Effort-Expenditure for Rewards Task (EEfRT) is a multi-trial game in which participants are given an opportunity on each trial to choose between two different task difficulty levels in order to obtain monetary rewards.

Study #1: Description of Research Procedures, Monitoring for Safety and Minimization of Risks: Patients with OUDs will undergo stimulation at the different parameters outlined. Subjects will first be outfitted with wearable sensing devices (patches attached to the chest and arms) for measurement of physiological signals including the electrical rhythm of the heart (electroencephalogram) as shown in the figures. These figures outline how parameters of interest like PEP and PPG amplitude are measured. Craving is measured with visual analogue scales. Patients will undergo VNS or sham stimulation while viewing neutral and opioid use related videos.

6.4 Magnetic Resonance Imaging (MRI) of the Brain: Subjects in both Study #1 and Study #2 will undergo MRI brain imaging at CSI for identification of the vagus nerve in the neck. Sequences to be obtained include volumetric interpolated breath-hold examination (VIBE), TR=4.93, TE=2.46, flip angle=9, Field of View 210 mm, 112 slices, voxel .78 x .78 x .8, averages 3, time of acquisition 4:38. 3D constructive interference in steady state (CISS), TR=5.46, TE=2.43, flip angle=42, Field of View 152 mm, 112 slices, voxel .6 x .6 x .6, averages 1, time of acquisition 5:17.

6.5

For Study #2 we look at physiology with nVNS or sham in OUD patients. Brain function will be measured with high resolution positron emission tomography (HR-PET) (264-270), autonomic function with wearable sensing devices, and biomarkers will be measured in blood, with an assessment of a broad range of stress responsive sympathetic, hormonal and immune markers. A

complete outline of study procedures for Study #2 is presented in Figure 4.

After initial set up and rest period subjects will rest for 30 min. Next, subjects will undergo a series of viewing exercises while lying in the High Resolution Positron Emission Tomography (HR PET) scanner with physiologic monitors attached. After an initial baseline period of resting (condition 1), the subjects will then view two neutral 120 second videos (condition 2), followed by a playback of two opioid use related videos (condition 3). The subject will be instructed to image each event as vividly as possible. VNS or sham will be randomized and given during exposure to the videos. For two of the scans, we are looking at effects of nVNS on the brain with no intervention. The subjects will undergo nVNS vs. Sham VNS stimulation as per published methods (see above).

The VAS and SUDS and other behavioral measures are assessed in the beginning and after each task to assess the efficacy of the

[figure not shown]

Figure 2: Measurement of physiological signals using wearable sensing devices in conjunction with nVNS/sham in human subjects. nVNS or sham are attached with a strap to the neck and for electrical stimulation of the vagus nerve as it passes through the carotid sheath. Electrocardiogram (ECG) and seismocardiogram (SCG) are placed on the chest for measurement of heart function and photoplethysmogram (PPG) placed on the finger measures blood volume/peripheral vasoconstriction. The ECG measures the distance on a beat-by-beat basis of the R wave interval (ventricular depolarization, which allows measurement of heart rate (HR) and with SCG pre-ejection period (PEP) as described in Figure 3). Sensing devices on the hand measure electrodermal activity (EDA), with output of skin conductance level (SCL), a marker of sympathetic function. A band on the chest measures respiratory rate (RR), width (RW), and prominence (RP) which tracks parasympathetic function. Data is reduced and analyzed and machine learning models are applied to predict the stimulation type (nVNS or sham). Subjects also undergo brain imaging with High Resolution sPositron Emission Tomography (HR-PET) in Study #2 and magnetic resonance imaging (MRI) of the brain in both studies

[figure not shown]

Figure 3. ECG measures electrical activity of the heart (See Fig. 2) and SCG measures chest wall movements used to register cardiac function including Aortic valve opening (Ao). The time interval between the R wave and Ao is PEP, which shortens with increased cardiac sympathetic tone. The difference in PPG amplitude (see Fig. 2) between time points measures vasoconstriction, an indicator of increased sympathetic function.

PROTOCOL TITLE: Non-invasive Vagal Nerve Stimulation in Opioid Use Disorders

trauma recall task in eliciting stress. Patients will stay at the Emory University Center for Systems Imaging while they are undergoing detailed autonomic monitoring and sampling of blood biomarkers. *The blood draws will occur at baseline, 15 minutes before the drug cue task, during the task itself, and then 15, 30, 45, 60, 90, and 120 minutes post-task.*

The “VNS” group will be administered nVNS using the electroCore GammaCore-S non-invasive VNS device. The intensity of the stimulus (i.e. the current amplitude) will be adjusted by the user, to the maximum tolerable level to ensure nVNS without causing excessive pain (typically 10-30 V), the burst frequency to 5 kHz, and the envelope frequency to 25 Hz. These are the standard frequency settings that electroCore has demonstrated to be most effective in capturing the vagus nerve based on evoked potential studies. The duration of delivery will be 2 minutes, and the beginning will coincide with initiation of acquisition of the HR-PET scan which will be 90 seconds in duration; following an additional 8 minutes, a second VNS delivery will be administered, in conjunction with which another scan will be obtained. Each subject in the “SHAM” group will undergo the action of administering the intervention, but the device will be programmed such that the vagus nerve is not actually stimulated.

6.6 Procedures Performed to Lessen Probability or Magnitude of Risks:

- Psychological Assessments: There is a risk that patients may become more upset as a result of being administered questionnaires or assessments. If this occurs they will be assessed by the research coordinator and if needed [name] or one of the other study psychiatrists on the protocol. If deemed clinically appropriate they will be assessed with the Sheehan Suicidality Scale and if there is a score greater than 0 escorted to the Emergency Room for further evaluation
- Intravenous Catheters and Venipuncture: Placement of an intravenous catheter can result in infection, bruising of the skin, or a blood clot in the vein. The risk of these complications occurring will be reduced by having the procedures performed by a professional under clean conditions and using sterile procedures. Dizziness and fainting are rare risks of blood draws that will be reduced by having the subject supine. There are no long-term side effects.
- Vagal Nerve Stimulation: Stimulation of the vagus nerve may cause muscle twitching, discomfort, or pain during treatment. Hoarseness, a change in voice, or change in taste are other temporary possible consequences but

PROTOCOL TITLE: Non-invasive Vagal Nerve Stimulation in Opioid Use Disorders

these resolve when treatment is stopped. These risks will be minimized by stopping the procedure or reducing the intensity of the stimulation

- H₂[15O] and PET: H₂[15O] or radiolabeled water has been administered to thousands of subjects without side effects or toxicity to date at the doses to be used in this study. [name] holds an IND for use of radiolabeled water at Emory University. H₂[15O] is a radioactive materials. Each patient will have eight H₂[15O] blood flow scans. For each O-15 water scan 20 mCi of H₂[15O] will be injected as an intravenous bolus. The body organs which receive the highest dose of H₂[15O] is the intestine and gonads. The radiation dose to body organs in this study is well within the Food and Drug Administration (FDA) national guidelines for radiation exposure for human research studies and less than the total amount that is permitted for research studies in one year. Risk will be reduced by careful screening. The subjects will be asked if they have participated in research studies that involved radiation over the past year. Risks are reduced by the principles of ALARA, or As Low As Reasonably Allowable, which involves time (reducing time exposure), distance (keeping dose away from subject) and shielding (using lead shields to protect from radiation as much as possible). Risk will also be reduced by ensuring radiation administration is not greater than that outlined in the protocol, and which is below limits for a single session set by regulatory agencies, and that subjects do not participate in more than three research sessions with radiation in a 12 month period, also per guidelines. Also, they will be advised that they should not participate in other research studies involving radioactivity over the next year without consulting [name] first. There is a small risk of claustrophobia with PET. If needed the study will be stopped.
- MRI: Subjects can become claustrophobic in the scanner. If needed the study can be stopped or 1-2 mg lorazepam given by mouth. If there is indwelling metal in the head this can cause injury. Subjects will be screened for indwelling metal.
- Opioid Use Related Videos: Viewing videos about opioid use may result in an increase in opioid craving. Viewing videos on smart glasses may cause wooziness or motion sickness. The research staff will debrief subjects, which involves talking about the experiences and helping

[figure not shown]
PROTOCOL TITLE: Non-invasive Vagal Nerve Stimulation in Opioid Use Disorders

subjects to process whatever emotions come up for the subject. If needed, for example if the subject is experiencing suicidal thoughts, further action will be taken if necessary as outlined above. Risks will also be reduced by having the research coordinator talk about their thoughts and feelings and craving after exposure to the drug use video.

- Procedure for Protecting Against Potential Risks:
Supervision: All of the scans will be done in the presence of constant supervision with experienced research staff always in attendance and in an institution specifically designed, equipped and functioning in support of these type studies. In the event that some serious medical complications could occur, the PET scan facilities are located in Wesley Woods Hospital on the Emory University campus and can provide immediate care. Confidentiality: All of the information obtained from patients is quoted by number and kept locked in confidential files. This information is available to study investigators. Risk-Benefit Ratio: The risks of participation in this study are small. These are outweighed by the potential benefit which a better understanding of the effects of OUDs could have for society.

PROTOCOL TITLE: Non-invasive Vagal Nerve Stimulation in Opioid Use Disorders

- Adverse events (AEs) are evaluated at each visit and reported to IRB using standard Emory IRB reporting guidelines. Serious adverse events (SAEs) (as defined by

CRF 312.32) are reported to the IRB using standard Emory IRB reporting guidelines. All AE and SAE reports will include a description of the event, severity, relationship to the study medication or procedures, any intervention required, and date of the resolution of the event (or otherwise listed as ongoing). SAEs include any fatal event, immediately life threatening event, permanently or significantly disabling event, event requiring prolonged inpatient hospitalization, or any congenital anomaly, and any other event that deems to result in a significant hazard, contraindication, side effect or precaution.

Written IND safety reports will be submitted to the FDA by the IND sponsor, for serious, unexpected suspected adverse reactions within 15 calendar days of learning of its occurrence. If the event is fatal or is deemed to be life threatening, the report will be made within 7 calendar days. The IND sponsor will also make an assessment of whether the event constitutes an unanticipated problem posing risks to subjects or others (UP). This assessment will

[figure not shown]
PROTOCOL TITLE: Non-invasive Vagal Nerve Stimulation in Opioid Use Disorders

be provided to the Emory University IRB, which, in turn will make a final determination. If the Emory IRB determines an event is a UP it will notify the appropriate regulatory agencies and institutional officials.

- All non-compliance/unanticipated problems, serious adverse events, audits and investigation reports will be reported to the Emory IRB following the standard reporting obligations.
- NVNS devices are provided by ElectroCore Inc, are FDA approved for the treatment of headache, and currently approved by the Emory IRB for the study of PTSD with demonstrated safety and efficacy.
- Included are all surveys and questionnaires. Data stored include information from surveys and questionnaires and all data are stored in the Emory Redcap system.

PROTOCOL TITLE: Non-invasive Vagal Nerve Stimulation in Opioid Use Disorders

6.7 Data Collected and Method of Attainment: Data is collected with surveys and questionnaires and stored securely in the Emory Redcap system. Other

data collected include blood for measurement of biomarkers, brain imaging data and wearable sensing device (autonomic function) data. Data is kept on secured Emory servers and under double lock and key in EP12 Emory Clinic Psychiatry and the CSI.

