11.0 Vulnerable Populations* N/A

12.0 Local Number of Participants

12.1 Study #1 will be to optimize dosing (N=20) and Study #2 to measure brain and biological correlates of nVNS versus sham in conjunction with exposure to drug use cues (N=20).

12.2 We will ask IRB to approve 60 enrollees (total) in order to account for some screen failures. We would like to have 20 in each study to complete research procedures.

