17.0 Data Management* and Confidentiality

17.1 We will use analysis of variance models with change in blood flow as dependent variable and absolute blood flow during control task as well as study group as explanatory variables. This analysis will assess differences in brain function according to diagnosis correcting for potential differences in baseline (control task) values. The ANOVA model will be blocked by the matching factor of past alcohol exposure. Analyses will be adjusted for whole brain blood flow. Additional control factors, including patients' age, age of onset of traumatization, years of education, IQ, OUD symptom level and duration of disease, use of oral contraceptive birth control, and smoking, will be entered in the model if they are significantly different between the study groups at an alpha level of 0.25, and/or if they are found to be confounders in the analysis, i.e., if they cause a change of >10% in the parameter estimate for study group when entered in the model. Adjusted means of blood flow will be computed for each combination of group and task to better describe the results. Point estimates and confidence intervals for the difference between groups will be assessed before and after including the covariates mentioned above in the model. Additional analyses will compare OUD patients with and without a history of co-morbid depression.

In all these analyses linear model assumptions, adequacy of fit, and presence of outliers will be checked by inspecting residual plots and influence statistics. Collinearity for variables included in the model will also be checked. Appropriate remedies will be applied, if necessary, to improve model fit and minimize collinearity.

Additional exploratory analyses will use subtraction analysis techniques to look for additional areas of activation for the purpose of generating hypotheses for future studies. Images of absolute blood flow will be subjected to a subtraction type analysis. Images will be realigned to the first image in the series and warped into a common anatomical space using methods described in the preliminary results. Images will be then analyzed using the general linear model of Friston for statistical analysis. The mean of blood flow scans within condition will be calculated and comparisons performed between conditions to assess blood flow with the condition. Areas of increased and decreased blood flow within patient group will be examined, as well as the interaction between

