PROTOCOL TITLE: Non-invasive Vagal Nerve Stimulation in Opioid Use Disorders

condition and diagnostic group. Images of t statistic will be created and surveyed for hypothesized regions (i.e. medial prefrontal cortex) where uncorrected z score values are greater than 2.86 (corresponding to a corrected p value of > 0.005).

Calculation of Sample Size

For calculation of sample size needed for PET measurement of anterior cingulate activation, we used values for blood flow in the amygdala (scaled to whole brain blood flow) based on previous pilot data. Fear-related tasks resulted in a $6.9 + 4.8\%$ increase in amygdala blood flow versus $1.2 + 1.4\%$ in controls (effect size 1.39). With two tails, an alpha value set at 0.05 and a power of 0.80, 10 subjects are needed in each group (VNS v sham) to show a significant difference between patients and controls (i.e. group by condition interaction). The number of subjects in each group will therefore be adequate to answer the questions proposed in this study.

- 17.2 All study staff will take required training prior to working with participants and/or PHI. All data will be kept in either locked offices in secure buildings or online via Redcap or on a password restricted research server. A certificate of confidentiality will be in place. Confidentiality will be assured by the use of subject codes when possible rather than personal identifiers. After the study is completed, the study database will be secured, and information will only be entered using subject identifier codes rather than personal identifiers. Published results will be presented as group data, without identifiers.
- 17.3 A (bi) weekly meeting with the staff, Study Coordinator and the PI is held to discuss any issues that may arise. A review of data is done for accuracy and protocol compliance. Data collection forms are verified for accuracy before storing in database. Describe any procedures that will be used for quality control of collected data.
- 17.4 Describe how data or specimens will be handled study-wide:
 - Study ID, date of visit, and type of sample will be included for each specimen
 - Specimens will be stored in a -80 freezer at EP12 or RSPH
 - Specimens will be stored until they are fully utilized for testing
 - The [name] Lab and the study team will have access to the data and/or specimens

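### Study #2 needs 10 subjects per arm out of 20, but the allocation text gives no ratio, block or balancing rule to secure that split

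*Combined protocol and SAP*

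**What the plan says.** **Allocation (section 6.2).** "Active and sham devices are assigned serial numbers by ElectroCore Inc. and delivered to the Data Manager". This role also holds the treatment codes. The only allocation rule given is that the manager "assigns to subjects as they are recruited using a random number generator". The section does not state a ratio, a list, a block size, a stratification factor or how many devices of each type are supplied. Section 6.5 adds only that the stimulation type is randomised.

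**Numbers (sections 12.2 and 17.1).** Section 12.2 sets the target in completers: "We would like to have 20 in each study to complete research procedures". The sample size paragraph of 17.1 works "With two tails, an alpha value set at 0.05 and a power of 0.80" and concludes that "10 subjects are needed in each group (VNS v sham"). The effect size is taken from pilot amygdala data, a fear-related "increase in amygdala blood flow versus" a smaller one "in controls (effect size 1.39").

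**Analysis (section 17.1).** "We will use analysis of variance models with change in blood flow as dependent variable", with control-task flow and study group as explanatory variables. Residual plots and influence statistics are to be inspected and remedies applied if needed. No remedy is named.

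**The concern.** The sample size calculation assumes two arms of exactly 10, and 20 completers leave nothing over. The only allocation rule given does not produce that split by itself. With so few subjects, independent draws usually give unequal arms, and an imbalance cannot be undone once subjects have been assigned. At stake is power for the PET comparison between nVNS and sham, in a phase whose results decide whether the larger UH3 study goes ahead.

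A secondary, conditional issue concerns the test itself. An analysis of variance with one common residual variance tolerates unequal spread well when the arms are equal in size, and less well when they are not.

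**Working it through.** **Inputs.** Total N = 20 (12.2); 10 per arm, two-sided alpha 0.05, power 0.80 and effect size d = 1.39 (17.1). I take d as stated and do not test here whether it suits the anterior cingulate. Assumption: each subject is an independent 50:50 draw, which 6.2 neither states nor excludes.

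**1. The plan's own figure.** The normal approximation gives n = 2(1.960 + 0.842)² / 1.39² = 8.1, so 9 per arm. With the noncentral t distribution, power is 0.790 at 9 per arm and 0.836 at 10. The stated 10 per arm is reproduced.

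**2. How often simple randomisation gives 10:10.** With k subjects on nVNS, P(k) = C(20,k)/2²⁰, and 2²⁰ = 1,048,576.

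- Exactly 10:10: 184,756 / 1,048,576 = 17.6%
- 8:12 or worse: 2 × 263,950 / 1,048,576 = 50.3%
- 7:13 or worse: 2 × 137,980 / 1,048,576 = 26.3%
- 6:14 or worse: 2 × 60,460 / 1,048,576 = 11.5%

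**3. Power at each split.** The noncentrality parameter is 1.39 × √(n₁n₂/20) on 18 degrees of freedom.

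| Split | Noncentrality | Power |
|---|---|---|
| 10:10 | 3.11 | 0.836 |
| 8:12 | 3.05 | 0.821 |
| 7:13 | 2.97 | 0.801 |
| 6:14 | 2.85 | 0.769 |
| 5:15 | 2.69 | 0.721 |

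Weighted by the binomial probabilities, average power is 0.815. Forcing 10:10 adds 0.836 − 0.815 = 0.021. Power drops below 0.80 only at 6:14 or worse.

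**4. Secondary check on type I error, conditional on unequal spread.** Suppose stimulation changed the spread of the response but not its mean, and borrow the pilot figures 4.8 and 1.4, read as SDs, for the two arms. Numerical integration of the pooled two-sample t-test at a nominal 5% gives 6.0% at 10:10 and 7.2% averaged over binomial splits. With equal SDs it is 5% at any split.

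A simulated covariate-adjusted model with the same SDs (one covariate, 20,000 runs) shows that the choice of robust standard error matters. At 10:10 the ordinary test rejects 6.1%, HC0 8.3%, HC1 6.4% and HC3 4.7%. At 7:13 HC1 rejects 8.6%.

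**The case against.** **The method may already be balanced.** A random number generator can produce a blocked list, and drawing without replacement from 10 active and 10 sham devices would also force 10:10. Section 6.2 excludes neither. This stands: the 17.6% is conditional on simple randomisation, and a reader should not take it as established that allocation is unrestricted. The firm finding is that no balancing rule is written down.

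**The power loss is small.** This also stands. Average power stays above 0.80, and 7:13 still reaches 0.801.

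**A tempting stronger reading.** Putting the unequal pilot SDs together with unequal arms, a reader might infer that the 5% test really runs at 15% to 19%. With those SDs the pooled test does reject 14.8% at 7:13 and 19.0% at 6:14 when the more variable arm is the smaller one. The documents do not support this as a property of Study #2, for three reasons.

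- The SDs describe pilot amygdala flow in a fear task and in controls. They are not SDs of nVNS and sham arms, nor of the anterior cingulate.
- Both arms are randomised from one OUD population. If nVNS has no effect, their variances are equal and the test holds at 5%. Inflation needs a change in spread with no change in mean.
- Even granting the SDs, 7 or fewer in the more variable arm has probability 13.2% under simple randomisation. The reverse splits are conservative (1.6% at 13:7, 0.9% at 14:6).

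Section 17.1 also commits to checking model assumptions, which partly covers unequal spread, although the remedy is left open.

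**Conclusion.** The point holds as a gap between the allocation text and the sample size. The plan needs 10 per arm from 20 completers and states nothing that secures it. On the natural reading of 6.2, the planned split would occur in 17.6% of allocations, and 11.5% would leave power at 0.769 or less against the stated 0.80. The expected cost is about two percentage points of power. These figures assume independent 50:50 assignment and the plan's effect size of 1.39.

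The type I error issue is secondary. It arises only if stimulation alters spread without altering the mean. Under the pilot SDs the average is 7.2%, against about 6% with balanced arms, so balance removes most of the excess due to unequal arm sizes.

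This is modest in size but more than a reporting detail, because a better method is available at almost no cost and has to be in place before subjects are assigned.

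**What to change.** In section 6.2, state a 1:1 ratio and have the Data Manager assign serial numbers from a pre-generated, concealed permuted-block list with varying block sizes that sum to 20 (for example 4, 6, 4 and 6 in random order). If a balanced list or a fixed device pool is already intended, say so.

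Add a rule for replacing non-completers within the list, because section 12.2 counts completers and section 15.1 notes that someone who cannot finish the first PET scan may not continue. Blocking balances those randomised; it does not guarantee 10:10 among completers.

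If a robust standard error is added to the covariate-adjusted model in 17.1, name a small-sample version such as HC3. An unnamed one could do worse than the ordinary test at 10:10.

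The cost is one list and a few sentences. The drawback is slight predictability near the end of a block, limited by concealment and varying block sizes.
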